Safety Assessments:	Reactogenicity will be assessed daily on each vaccination day and the following 7 days via collection of solicited local adverse events (AEs; injection site pain, redness, swelling, and itching) and systemic AEs (fever, headache, fatigue, chills, myalgia, arthralgia, nausea/vomiting, and diarrhea) using diary cards (electronic or paper). In addition, other indicators of safety will be collected (e.g., body temperature). Diaries will also be used for collection of unsolicited AEs on each vaccination day and the following 28 days. In addition, subjects will receive a prompt (by e.g., a phone call or text message) to verify whether the subjects had any health concerns since the last visit. Subjects with any Grade 3 solicited or unsolicited AEs reported electronically by the subject will be contacted by the Investigator, and subjects who did not enter any diary information will be prompted and then contacted in case of non-response within 24 hours. Unscheduled visits will be performed when deemed necessary for safety assessments or to ensure data integrity. SAEs, adverse events of special interest (AESIs), and AEs leading to vaccine withdrawal or trial discontinuation will be collected throughout the trial. Non-serious intercurrent medical conditions that may affect the immune response to vaccination will also be collected throughout the trial. AESIs to be monitored throughout the trial include potential immune-mediated diseases (pIMDs) and COVID-19 disease. In case of confirmed COVID-19 disease, a disease-specific diary will be completed by the subject and/or the treating health care provider.
Laboratory Testing for COVID-19 Disease:	As a baseline assessment, a reverse transcription polymerase chain reaction (RT-PCR) test for SARS-CoV-2 will be performed in all subjects. Testing will be done for SARS-CoV-2 spike protein to evaluate vaccine-induced immune responses as well as for SARS-CoV-2 N-antigen (not contained in the vaccine construct) to evaluate immune responses induced by natural infection. This will allow to retrospectively define the subject's serology status, including the baseline status for the by-group/cohort analysis. Subjects will be prompted once or twice per week to report if the subjects have any of the following symptoms: cough, shortness of breath, difficulty breathing, fever $\geq 37.8^{\circ}\text{C}$, fatigue, myalgia, chills, wheezing, nasal congestion, runny nose, sore throat, headache, diarrhea, or new olfactory

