3.2 Trial Rationale

In partnership with the Coalition for Epidemic Preparedness Innovations (CEPI), CureVac AG is developing a new SARS-CoV-2 messenger ribonucleic acid (mRNA) vaccine formulated with lipid nanoparticles (LNP), referred to as CVnCoV, for the prevention of COVID-19 disease when administered as a 2-dose primary vaccination schedule. CVnCoV was developed with CureVac's proprietary RNAActive® technology platform, which uses chemically unmodified mRNA molecules as a basis for vaccination. The safety and immunogenicity of this vaccine was evaluated for the first time in humans in the dose-finding trial CV-NCOV-001.

This second trial was conducted to confirm the safety and immunogenicity of CVnCoV at different dose levels in adults >60 years of age (i.e., 61 years or older) when administered according to a 0 (Day 1), 1-month (Day 29) primary vaccination schedule. The dose levels to be administered in this trial will be selected based on data from Trial CV-NCOV-001. For this elderly population, higher dose levels than the dose levels investigated for adults 18 to 60 years of age will be considered to address potentially reduced immunogenicity in

the context of immunosenescence. In addition, the safety and immunogenicity of a booster dose of CVnCoV administered at approximately 2 months (Day 57) or 6 months (Day 180) after the first dose will be evaluated in a subgroup of subjects.

In order to bridge to the population evaluated in Trial CV-NCOV-001, adults 18 to 60 years will also be enrolled in this trial.

[figure not shown]
For further clinical development and for the expansion cohorts, the selected dose of 12 µg will generate comprehensive safety and immunogenicity data for CVnCoV.

[figure not shown]
Please refer to the Investigator's Brochure for details on the RNAActive® technology, information regarding the non-clinical studies of the investigational CVnCoV vaccine, and additional information.

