9.1.1.3 Adverse Events of Special Interest

The following events will be considered as AESI during this trial:

- AEs with a suspected immune-mediated etiology (pIMDs, see Appendix 8),
- COVID-19 disease,
- other AEs relevant to SARS-CoV-2 vaccine development or the target disease (see Appendix 9).

AESIs will be collected throughout the trial.

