### 9.4 Estimands

ENDPOINTS (subject level)	ESTIMANDS (population level)
Primary Safety	

The frequencies, intensities, and duration of solicited local AEs on Day 1 and Day 29 and the following 7 days by dose and group.
 
The frequencies, intensities, duration, and relationship to trial vaccination of solicited systemic AEs on Day 1 and Day 29 and the following 7 days by dose and group.
 
The occurrence, intensity and relationship to trial vaccination of unsolicited AEs on each vaccination day and the following 28 days by dose and group.
 
The occurrence and relationship to trial vaccination of SAEs and AESIs throughout the trial.
	
Safety set. Subjects who were unblinded and/or received an authorized/licensed COVID-19 vaccine will be censored at the day after unblinding and/or vaccination receipt.
 
The number and percentage of subjects overall and by dose level:
 
Each solicited local AE within 7 days after each trial vaccination by intensity and overall.
 
Each solicited systemic AE within 7 days after each trial vaccination by intensity, by relationship to trial vaccine and overall.
 
The mean duration in days by group with standard deviation of solicited AEs (within the solicited period, total duration).
 
At least 1 unsolicited AEs, at least 1 grade unsolicited AEs and each unsolicited AEs by SOC/PT occurring within 28 days after each trial vaccination and overall by causal relationship to trial vaccine and overall.
 
At least 1 SAE, or at least 1 AESI to vaccine overall by causal relationship to trial vaccine and overall.

ENDPOINTS (subject level)	ESTIMANDS (population level)
Primary Immunogenicity	

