#### 10.5.5 Adverse Events of Special Interest

The following events will be considered as AESI during this trial:

- AEs with a suspected immune-mediated etiology (pIMDs, see Appendix 1),
- COVID-19 disease,
- other AEs relevant to SARS-CoV-2 vaccine development or the target disease (see Appendix 2).

AESIs will be collected on eCRF throughout the trial

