### 12.8.1 Analysis of Unsolicited and Solicited AEs

An overall summary of unsolicited AEs will be prepared for AEs occurring within 28 days after each dose, within 28 days after any dose, and all reported AEs (including those reported at more than 28 days after any dose), presenting the number and percentage of subjects with

---

- Unsolicited AEs
- related unsolicited AEs
- grade 3 (severe) unsolicited AEs
- grade 3 (severe) related unsolicited AEs
- SAEs (includes solicited AEs)
- related SAEs (includes solicited AEs)
- intercurrent medical conditions affecting immune response (includes solicited AEs)
- AESIs (includes solicited AEs)
- related AESIs (includes solicited AEs)
- medically attended AEs (includes solicited AEs)
- related medically attended AEs (includes solicited AEs)
- AEs leading to vaccine withdrawal (includes solicited AEs)
- AEs leading to withdrawal from trial (includes solicited AEs)

The overall summary will also be presented by sex (female/male) for any dose regardless of retrospective serology status at baseline.

The following summaries of AEs by SOC and PT will further be provided, separately for AEs occurring within the first 28 days after each vaccination, within the 28 days after any vaccination, and all reported AEs (including those reported at more than 28 days after any dose) if not otherwise stated:

- Occurrence of unsolicited AEs
- Occurrence of related unsolicited AEs
- Occurrence of unsolicited AEs by maximum severity (mild / moderate / severe)
- Occurrence of related unsolicited AEs by maximum severity (mild / moderate / severe)
- Occurrence of SAEs (includes solicited AEs)
- Occurrence of related SAEs (includes solicited AEs)
- Occurrence of SAEs by maximum severity (mild / moderate / severe) (includes solicited AEs)
- Occurrence of related SAEs by maximum severity (mild / moderate / severe) (includes solicited AEs)
- Occurrence of intercurrent medical conditions affecting immune response (includes solicited AEs)
- Occurrence of AESIs (includes solicited AEs)
- Occurrence of related AESIs (includes solicited AEs)
- Occurrence of medically attended AEs (includes solicited AEs)
- Occurrence of related medically attended AEs (includes solicited AEs)
- Occurrence of AEs leading to vaccine withdrawal (includes solicited AEs)
- Occurrence of AEs leading to withdrawal from trial (includes solicited AEs)
- Occurrence of AEs related to SMQs as defined in Section 10.5.9 (includes solicited AEs)

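### The primary count of subjects with any AESI pools COVID-19 disease with immune-mediated and other events, so its all-causality percentage can dilute, and under some assumed rates reverse, a difference in non-COVID AESIs.

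*SAP*

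**What the plan says.** SAP 9.4 lists the primary endpoint as "The occurrence and relationship to trial vaccination of SAEs and AESIs throughout the trial" and turns it into a subject count: "At least 1 SAE, or at least 1 AESI to vaccine overall by causal relationship to trial vaccine and overall".

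SAP 10.5.5 builds AESI from three parts. The first is "AEs with a suspected immune-mediated etiology (pIMDs, see Appendix 1"), the second is COVID-19 disease, and the third is "other AEs relevant to SARS-CoV-2 vaccine development or the target disease (see Appendix 2"). Protocol 9.1.1.3 has the same three parts, the third being "other AEs relevant to SARS-CoV-2 vaccine development or the target disease (see Appendix 9"). The protocol synopsis puts it more briefly: "AESIs to be monitored throughout the trial include potential immune-mediated diseases (pIMDs) and COVID-19 disease". SAP Appendix 2 names COVID-19 disease again among the respiratory disorders, so COVID-19 enters the definition twice.

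Protocol 3.2 describes CVnCoV as being developed "for the prevention of COVID-19 disease when administered as a 2-dose primary vaccination schedule".

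SAP 12.8.1 repeats the any-AESI and related-AESI counts in its overall summary. It then gives tables by SOC and PT, including "Occurrence of AESIs (includes solicited AEs"), within 28 days of each dose, within 28 days of any dose, and for all reported events. SAP 12.0 places CVnCoV, active control and total in the same tables. Neither document specifies a count of subjects with any non-COVID AESI, or of subjects with a pIMD as defined in Appendix 1.

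**The concern.** The components of this count can move in opposite directions. A vaccine that works lowers the COVID-19 part, while a vaccine-related harm raises the pIMD or other part. Adding them in one subject-level count lets the first conceal some or all of the second.

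The COVID-19 part is also the one that is actively sought. Protocol 9.3 has subjects prompted once or twice a week for symptoms, with testing to follow; no comparable prompting is described for pIMDs.

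The trial is descriptive, so the tables are the result. A reader who takes the all-causality AESI percentage as a measure of harm, and compares the CVnCoV and control columns, would be reading a mixture of efficacy and safety.

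**Working it through.** **The plan's own figures.** The documents state no expected AESI rate, COVID-19 rate, vaccine efficacy or precision for AESIs, so there is no figure to reproduce on this point. Every rate below is an assumption.

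**Sample sizes (protocol Table 5, SAP Table 2).**
- CVnCoV: 11 + 12 + 90 + 90 + 200 + 200 = 603.
- Active control: 10 + 10 + 40 = 60.

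**Formula.** Let c be the control COVID-19 rate, VE the efficacy, h the control rate of other AESIs, and RR the true ratio for other AESIs. If COVID-19 and other AESIs are independent within a subject:
- control composite = 1 − (1 − c)(1 − h)
- CVnCoV composite = 1 − (1 − c(1 − VE))(1 − h·RR)

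**Illustration: c = 5%, VE = 50%, h = 1%, RR = 2.**
- Control: 1 − 0.95 × 0.99 = 5.95%.
- CVnCoV: 1 − 0.975 × 0.98 = 4.45%.
- Ratio: 4.45 / 5.95 = 0.75, although the non-COVID ratio is 2.0.

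**Range, keeping h = 1% and RR = 2.**

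| c | VE | Control | CVnCoV | Ratio |
|---|---|---|---|---|
| 1% | 50% | 1.99% | 2.49% | 1.25 |
| 2% | 50% | 2.98% | 2.98% | 1.00 |
| 5% | 0% | 5.95% | 6.90% | 1.16 |
| 5% | 50% | 5.95% | 4.45% | 0.75 |
| 10% | 50% | 10.90% | 6.90% | 0.63 |

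The true doubling is diluted in every row, including the one with no efficacy. The direction reverses only in the last two.

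**When does it reverse?** The expected rates reverse if VE > h(RR − 1)(1 − c) / [c(1 − h·RR)]. With h = 1% and RR = 2:
- c = 1%: 0.0099 / 0.0098 = 101%, so never
- c = 2%: 0.0098 / 0.0196 = 50%
- c = 5%: 0.0095 / 0.049 = 19%
- c = 10%: 0.0090 / 0.098 = 9%

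**Sampling variation.** These are exact binomial results with 603 and 60 subjects, for the illustration (c = 5%, VE = 50%). The chance that the observed CVnCoV percentage lies below the observed control percentage is 67% on the composite. On non-COVID AESIs alone it is 23%. Separating the components helps, but does not make the contrast precise: with a 1% control rate, the chance of no non-COVID AESI at all among 60 controls is 0.99^60 = 55%.

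**Can the missing count be rebuilt from PT rows?** Not exactly, because one subject can appear in several rows. Under independence and the illustration rates, the expected number with both COVID-19 and another AESI is 603 × 0.025 × 0.02 = 0.30 on CVnCoV and 60 × 0.05 × 0.01 = 0.03 on control. Independence understates this where Appendix 2 events such as ARDS, anosmia or ageusia are recorded as part of a COVID-19 illness. Subjects with several non-COVID terms also prevent simple addition of the remaining rows.

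**The case against.** The strongest reply is that the rest of the planned output already separates most of this.

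- AESIs and related AESIs are tabulated by SOC and PT, so COVID-19 is visible as its own term (SAP 12.8.1).
- SAP 10.5.9 defines an immune-mediated/autoimmune SMQ, together with anaphylactic, convulsion, embolic/thrombotic, hypersensitivity and liver queries. SAP 12.8.1 tabulates them independently of the AESI count.
- RT-PCR-confirmed infection is counted separately on the safety set (SAP 12.9.5), and adjudicated cases are listed (SAP 10.9).
- The estimand is itself split by relatedness, and an investigator is unlikely to attribute COVID-19 to the vaccine.
- Listings allow a manual count, and under independence the overlap is below one subject.
- COVID-19 belongs among the AESIs for a safety reason: enhanced disease is on the Appendix 2 list.

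All of this stands, and it limits the point to the all-causality headline count. A reader might infer that the plan cannot show immune-mediated or other harms; the tables just listed contradict that.

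What the reply does not supply is the subject-level number. PT rows do not add up to it. The SMQ is neither the Appendix 1 list nor the third AESI component. The infection count isolates infection rather than the remaining events. The related rows depend on investigator judgement, whereas the value of a control arm is an all-causality comparison, and that is the row affected.

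A reader might also infer that reversal is to be expected because COVID-19 will make up most AESIs. The documents give no rates to support that. Exclusion criterion 19 removes people judged to be at increased exposure risk, and SAP 10.8 censors safety data from the day after unblinding. Both could keep the COVID-19 rate low.

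**Conclusion.** The point holds for one output: the all-causality count of subjects with at least one AESI, in SAP 9.4 and the overall summary of SAP 12.8.1. As specified, that percentage is not interpretable as harm, because it falls when COVID-19 falls.

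Dilution needs only that COVID-19 contributes to the count: at 5% COVID-19 and no efficacy a true doubling appears as a ratio of 1.16. Reversal is conditional. At other AESIs of 1% and 2% it needs efficacy above about 19% at 5% COVID-19 and above 50% at 2%, and cannot occur at 1%. These figures rest on assumed rates and on independence of the components.

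The importance is low to moderate. The trial makes no confirmatory claim, about 60 controls cannot support a precise AESI comparison on any definition, and the components can largely be seen elsewhere. The plan does not propose to judge harm by comparing the headline percentages, and nothing here calls for removing COVID-19 from the AESI definition or replacing the protocol's primary endpoint. The change is still worth making, because it adds the one missing number at almost no cost.

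**What to change.** In SAP 9.4 and the overall summary of SAP 12.8.1, keep the all-AESI row as the protocol-defined primary endpoint. Beside it add, with the same windows and relatedness split:

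1. subjects with at least one AESI excluding COVID-19 disease;
2. subjects with COVID-19 disease.

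A row for subjects with a pIMD as listed in Appendix 1 is optional.

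Define the exclusion with information the SAP already uses. SAP 12.9.5 removes COVID-19 cases classified as AESIs, and adjudicated cases, from the asymptomatic-infection analysis; the same flag serves here. State that Appendix 2 events recorded as manifestations of a confirmed COVID-19 case are counted with COVID-19, so that such a case does not reappear in the first row.

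The cost is one or two extra table rows and one definitional sentence. No new data are needed.

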Urine pregnancy test ^o	X				X				X ^g				X ^g					
TSH, thyroid antibodies, ANA (~3 mL) ^o	X																	
Nasopharyngeal swab collection for RT-PCR testing ^q	X																	
Immunogenicity^r																		
ELISA (serum) (~12 mL) ^s	X ^t				X ^t		X		X ^t		X		X ^{t,v}		X		X	
Only in subjects in the initial phase of the trial: SARS-CoV-2 neutralizing activity (serum) (~12 mL)	X ^t				X ^t		X		X ^t		X		X ^{t,v}		X		X	

Visit Number	Primary Vaccination Period								Booster Vaccination Period								End of Trial	
	1 ^a	2	Phone contact		3	Phone contact	4	Phone contact ^b	5 ^c	Phone contact ^c	6 ^c	Prompt	7	Phone contact ^d	8 ^d	Prompt	Phone contact	9 ^w
Visit Window (days)	n/a	-0/ +0	-0/ +0	-2/ +4	-2/ +4	-0/ +0	-2/ +4	-2/ +4	-2/ +4	-0/ +0	-2/ +4	-2/ +4	-10/ +10	-0/ +0	-2/ +4	-2/ +4	-0/ +30	-0/ +30
Trial Day	1	2	7 ^e	15	29	30	43	57	57	58	85	120	180	181	208	270	393	393
Anchoring	-	1	1	1	1	29	29	29	57	57	57	29	1	180	180	180	180	180
Subset of subjects from each CVnCoV group at predefined site(s): Cell-mediated immunity (~40-64 mL) ^u	X ^t				X ^t		X											
Subset of subjects from each CVnCoV group at predefined site(s): Cytokine assessment (serum) (~6 mL)	X ^t	X																
Maximum total blood volume (mL)	109	15			73		73		33		33		33		33			33
Trial end																		X

AE: adverse event; AESI: adverse event of special interest; ANA: antinuclear antibody; ECG: electrocardiogram; ELISA: enzyme-linked immunosorbent assay; Ig: immunoglobulin; RT-PCR: reverse transcription polymerase chain reaction; SAE: serious adverse event; TSH: thyroid-stimulating hormone

- Procedures to establish subject eligibility may be performed within 21 days prior to trial vaccine administration. If all information to establish eligibility is available, these procedures can be done on the same day including the trial vaccine administration. Eligibility criteria need to be reviewed on the day of vaccination prior to trial vaccine administration.
- Phone contact on Day 57 is not required for subjects receiving an open-label booster vaccination on Day 57.
- This will only take place for subjects receiving an open-label booster vaccination on Day 57.
- This will only take place for subjects receiving an open-label booster vaccination on Day 180.
- Phone contact can be made on Day 7 at the site's discretion to review the eDiary with the subject, but is not mandatory, and does not replace other scheduled phone contacts

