- q. Swabs for COVID-19 disease testing will also be collected in case the subject displays symptoms of acute respiratory infection (including, but not limited to COVID-19 disease), if operationally possible (see Section 9.3).
- r. See Section 9.2 for an overview of the immunogenicity assessments.
- s. ELISA will be performed on SARS-CoV-2 spike (S) protein to investigate immune responses to vaccination and on SARS-CoV-2 nucleocapsid (N) protein to determine immune response to natural infection.
- t. Baseline blood samples on Day 1, Day 29, Day 57, and Day 180 must be collected prior to vaccination.
- u. The blood volume to be collected for cellular immune response will be 64 mL on Day 1 and 40 mL on Days 29 and 43.
- v. Only for subjects receiving 6 µg and for subjects receiving the 12 µg booster dose on Day 57 or Day 180.
- w. Only for subjects who received the booster on Day 180 and who had not received a licensed/authorized vaccine before the End of Trial visit.

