### 6.1 Changes from Protocol

CMI response On Day 1, Day 29, and Day 43 in peripheral blood mononuclear cells (PBMCs) in a subset of subjects, will not be analyzed as part of this SAP, but listed only.

Evaluation of asymptomatic SARS-CoV-2 infection will be summarized by time point based on retrospective serology and RT-PCR results.

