
Evaluation of infection
 
 
Number of subjects with virologically-confirmed SARS-CoV-2 infection as measured by RT-PCR.
 
	
Subjects who were unblinded and/or received an authorized/licensed COVID-19 vaccine will be censored at the day after unblinding and/or vaccination receipt. Excluding subjects who had a COVID-19 infection at baseline.
 
Safety set.
 
The number and percentage of subjects by group at baseline and by post-baseline time points with a positive RT-PCR result

ENDPOINTS (subject level)	ESTIMANDS (population level)
PCR at clinically determined time points throughout the trial. 
 
Number of subjects with asymptomatic SARS-CoV-2 infection as measured by serology at predefined time points.
 
	Immunogenicity set. The number and percentage of subjects by group at baseline and post-baseline with a positive RT-PCR result and/or infection defined by SARS-CoV-2 N-antigen and no COVID-19 symptoms.

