### 10.6.1 Humoral Immune Response

In addition to evaluation of vaccine-induced immune responses, ELISA to SARS-CoV-2 N-antigen (not contained in the vaccine construct) will be performed to determine the subject's serology status to natural infection, to retrospectively identify the baseline serology status, and to detect and/or confirm natural infection during the trial. The SARS-CoV-2 N-antigen ELISA will be performed at the specified time points for humoral immune response testing to SARS-CoV-2 S-protein. See section 10.8 for more details related to censoring.

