#### 12.9.5 Additional Exploratory Analysis

Evaluation of infection:

Number and percentages of subjects with virologically-confirmed SARS-CoV-2 infection as measured by reverse transcription polymerase chain reaction (RT-PCR) at clinically determined time points throughout the trial. This analysis will be performed on the safety set.

Number and percentages of subjects with asymptomatic SARS-CoV-2 infection as measured by serology and RT-PCR test at predefined time points.

- The definition of SARS-CoV-2 infection as measured by serology and RT-PCR results before and during the trial is outlined in sections 10.6.3.
- Subjects with a COVID-19 disease symptoms are excluded. Exclusion is based on COVID-19 cases classified as AESI. Adjudicated cases are also excluded.

This analysis will be performed on the immunogenicity set.

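### Asymptomatic infection is tabulated by group after baseline, but after Day 43 scheduled N-antigen serology covers only boosted and 6 µg CVnCoV subjects and no controls

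*SAP*

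**What the plan says.** SAP 9.4 (Estimands, evaluation of infection) includes the endpoint "Number of subjects with asymptomatic SARS-CoV-2 infection as measured by serology at predefined time points". Its population-level summary is "The number and percentage of subjects by group at baseline and post-baseline with a positive RT-PCR result and/or infection defined by SARS-CoV-2 N-antigen", in subjects without COVID-19 symptoms. SAP 6.1 declares this as a change from the protocol: "Evaluation of asymptomatic SARS-CoV-2 infection will be summarized by time point based on retrospective serology and RT-PCR results". SAP 12.9.5 repeats it as "Number and percentages of subjects with asymptomatic SARS-CoV-2 infection as measured by serology and RT-PCR test at predefined time points" and adds: "This analysis will be performed on the immunogenicity set".

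SAP 10.6.1 fixes when the serology is run: "The SARS-CoV-2 N-antigen ELISA will be performed at the specified time points for humoral immune response testing to SARS-CoV-2 S-protein". The schedule of activities (Protocol Section 2, Table 1) gives the sampling days:

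- Days 1, 29 and 43: all subjects.
- Days 57 and 85: the footnote reads "This will only take place for subjects receiving an open-label booster vaccination on Day 57".
- Day 180: "Only for subjects receiving 6 µg and for subjects receiving the 12 µg booster dose on Day 57 or Day 180".
- Day 208: Day 180 booster recipients only.
- Day 393: Day 180 booster recipients who have not had a licensed or authorized vaccine.

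In the same table the RT-PCR swab is scheduled only on Day 1. Protocol 9.3 makes later testing depend on reported symptoms.

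**The concern.** An asymptomatic infection can be found only by testing someone who feels well. After Day 43 the plan does this on schedule for some CVnCoV subjects and for no controls, because neither the controls nor the expansion cohorts receive a booster (Protocol Table 2). The unboosted 12 µg subjects are not tested either. Yet the SAP asks for results by group and by time point after baseline, with no restriction to visits at which all groups are sampled and no statement of who forms the denominator at each visit.

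At stake is how one descriptive table is read. Differences between CVnCoV and control, and between CVnCoV groups, could come from who was tested. The direction would be unfavourable to the vaccine: more detected infection where there is more testing.

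**Working it through.** **1. Planned totals (Protocol Table 5, SAP Table 2).** CVnCoV: 11 + 12 + 90 + 90 + 200 + 200 = 603, the plan's own total. Control: 10 + 10 + 40 = 60.

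**2. Planned subjects with scheduled N-antigen serology after Day 43.** Booster subgroups (Protocol Table 2): 30 in Group 3 at Day 180, 30 in Group 4 at Day 57 and 30 in Group 4 at Day 180, so 90 boosted. The 6 µg groups: 11 + 12 = 23.

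| Visit | CVnCoV sampled | Share of 603 | Control sampled, of 60 |
|---|---|---|---|
| Day 57 | 30 | 5.0% | 0 |
| Day 85 | 30 | 5.0% | 0 |
| Day 180 | 23 + 90 = 113 | 18.7% | 0 |
| Day 208 | 60 | 10.0% | 0 |
| Day 393 | at most 60 | at most 10.0% | 0 |

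By group at Day 180: Group 1 11/11, Group 2 12/12, Group 3 30/90, Group 4 60/90, expansion CVnCoV 0/400. Sampling is therefore unequal among the CVnCoV groups too.

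**3. Scheduled serological window (Day 1 to last sample).** The 603 − 113 = 490 CVnCoV subjects without a later sample have 42 days, as do all 60 controls. The 23 on 6 µg and the 30 boosted at Day 57 (53 in all) have 179 days. The 60 boosted at Day 180 have up to 392 days.

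Mean for CVnCoV: (490 × 42 + 53 × 179 + 60 × 392) / 603 = 53,587 / 603 = 88.9 days, against 42 for control. Counting samples to Day 180 only: (490 × 42 + 113 × 179) / 603 = 67.7 days.

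**4. Effect with a full-set denominator.** Assumptions, not in the documents: the same asymptomatic infection risk r per month (30.4 days) in every group, full follow-up with no censoring, and N-antibody that persists to the last sample. A subject with window d days is detected with probability 1 − (1 − r)^(d/30.4), averaged over the numbers in step 3.

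Worked case, r = 1%: the probabilities are 1.38% (42 days), 5.75% (179) and 12.16% (392). CVnCoV: (490 × 1.38 + 53 × 5.75 + 60 × 12.16) / 603 = 2.84%. Control: 1.38%. Ratio 2.06.

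| r per month | CVnCoV | Control | Ratio | Ratio, samples to Day 180 only |
|---|---|---|---|---|
| 0.5% | 1.44% | 0.69% | 2.09 | 1.60 |
| 1% | 2.84% | 1.38% | 2.06 | 1.59 |
| 2% | 5.50% | 2.75% | 2.00 | 1.58 |
| 5% | 12.67% | 6.84% | 1.85 | 1.53 |

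The true ratio is 1.0 in every row. Under SAP 10.6.3 a positive status carries forward, so the status of untested subjects stays as it was at Day 43.

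**5. Effect with a number-tested denominator.** Control has n = 0 and no percentage from Day 57 on, and the CVnCoV figure describes boosted and 6 µg subjects only.

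**6. Restricted to Days 29 and 43.** The window is 42 days for all 603 and all 60, so the ratio under equal risk is 1.0.

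**The case against.** The strongest defence is that the SAP never says untested subjects enter the denominator. SAP 12.9.3 bases rates on the number available at the time point, and with that rule no control percentage would appear beside CVnCoV after Day 43. But that rule is written for seroconversion rates in the sensitivity analysis, while the general rule in SAP 12.8 (adverse events) uses the whole analysis set. Neither governs this table. A reader might infer that the SAP definitely counts untested subjects as uninfected. It does not say so, and the ratios in step 4 are conditional on that choice. Neither choice gives an interpretable comparison with control after Day 43.

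A reader might also infer that no N-antigen result can exist for any control after Day 43. That is true only of serology scheduled under protocol version 3.0. Samples taken under earlier versions may exist, and symptom-triggered local serology can make any subject positive under SAP 10.6.3. The latter does not screen symptom-free subjects.

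A third tempting inference is that the distorted percentages would be carried into pooled analyses. Protocol 10.3.1 speaks of pooling COVID-19 cases, and SAP 12.9.5 removes COVID-19 cases from this table, so the documents do not support it. Nor is bringing the analysis back an error in itself, since SAP 6.1 declares it.

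It also stands that the analysis is exploratory, that no inference is planned, and that Days 29 and 43 are sampled equally.

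**Conclusion.** The point holds as a mismatch between the table and the remaining sampling schedule. Days 1, 29 and 43 support a comparison between groups; later visits do not. The sampled numbers follow directly from the documents, with the Day 393 figure an upper bound. Protocol 4.2.2 lists Day 180 immunogenicity for booster recipients only; on that reading the Day 180 count is 90 instead of 113, and the conclusion is unchanged.

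The spurious ratio of about 1.9 to 2.1 (about 1.5 to 1.6 if only samples to Day 180 count) rests on a full-set denominator and the assumptions in step 4. Censoring at unblinding or licensed vaccination (SAP 9.4, 10.8) shortens late follow-up, so the ratio with samples to Day 393 is a no-censoring figure. The consequence is for interpretation of one exploratory table. It is a worthwhile correction and does not threaten the trial's main results.

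**What to change.** In SAP 9.4 and 12.9.5:

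- Limit the between-group table of asymptomatic infection to Days 29 and 43.
- Define the denominator at each visit as baseline-negative subjects with an N-antigen result at that visit, and print the number tested. The baseline-negative condition largely spells out the exclusion of baseline infections already in SAP 9.4.
- Present later visits only for the sampled boosted and 6 µg subgroups, with the number tested and no control comparison.

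The cost is a change of SAP wording and a visit filter, with no new data. The downside is small: infections after Day 43 are described only in the subgroups that were sampled.
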